### 8.3. Sample Size Considerations

A total of approximately 42 patients will be enrolled and randomized in order to achieve 34 patients who complete the study. Data from 34 patients provides 95.6% power to detect a statistically significant difference between the treatment groups in the primary endpoint (percent change from baseline in EASI scores). This power calculation is based upon a 1-sided treatment contrast within 1-way ANOVA model and assumes group means of 65% and 20% for ATI-1777 and vehicle, respectively. The group means were based upon slightly more conservative estimates than were observed in a Phase 2 study of topical ruxolitinib in AD. (Kim et al 2020b) The variance for the percent change from baseline in EASI was assumed to be 38.3%. This variance assumption was based upon data observed in a pilot AD study for the topical compound ATI-502 (ATI-502-AD-201).

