### 8.4. Randomization

At Visit 2, in the morning of Day 1, eligible patients will be randomly assigned in a 1:1 ratio via an interactive voice/web response system (IXRS) to ATI-1777 or vehicle treatment.

Enrolled patients will be allocated a unique patient number in a sequential order by trial site. Following randomization, Aclaris will provide all study medication in a packed and labelled kit, and the IXRS will identify the kit number to be dispensed to the patient at each relevant visit according to the treatment assigned in the randomization schedule.

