## 9.3. Predetermined Covariates and Prognostic Factors

The following factors will be adjusted as covariates:

- Baseline severity of AD (moderate vs severe)
- Continuous baseline severity EASI score/BSA score/IGA score
- Baseline BSA (3 to 10 vs greater than 10 to 20) to be used for PK spaghetti plots

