## 12. Statistical Methods

All analyses will use SAS version 9.4 or higher.

Categorical variables will be summarized using counts and percentages based on the specified population total. Percentages will be rounded to one decimal place, except 100% will be displayed without any decimal places and percentages will not be displayed for zero counts.

Continuous data will be summarized using non-missing observations (n, mean, standard deviation (SD), median, Quartile 1, Quartile 3, minimum, and maximum). The median, minimum, and maximum values will be displayed to the same level of the precision as the raw value. Mean, median, Q1 and Q3 will be rounded to 1 decimal place greater than the precision of the original value. The SD will be rounded to 2 decimal places greater than the precision of the original value. Confidence intervals, least square mean (LSM) and standard error (SE) will be provided as appropriate. Confidence intervals, LSM will present the same precision as the mean value whereas SEs will present the same precision as SD.

P-values will be rounded to 3 decimal places. P-values less than 0.001 will be presented as “<0.001” and p-values greater than 0.999 will be presented as “>0.999.”

Statistical hypothesis testing will be one-sided and carried out at the 5% level of significance. Testing will be performed on the primary endpoint and secondary endpoints as appropriate. No adjustments for multiplicity will be made.

If there is strong collinearity between the baseline EASI score/BSA score/IGA score and the baseline severity of AD (moderate versus severe), the continuous baseline score will be included the efficacy analysis.

All the listings will be displayed by treatment arm, patient identifier and date of assessment. Age, gender, and race will be presented on each listing.

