**Table 6 IGA Scoring**

| Score            | Morphological Description   |
|------------------|---|
| 0 - Clear        | No inflammatory signs of atopic dermatitis (no erythema, no induration/papulation, no lichenification, no oozing/crusting). Post-inflammatory hyperpigmentation and/or hypopigmentation may be present. |
| 1 - Almost clear | Barely perceptible erythema, barely perceptible induration/papulation, and/or minimal lichenification. No oozing or crusting.   |
| 2 - Mild         | Slight but definite erythema (pink), slight but definite induration/papulation, and/or slight but definite lichenification. No oozing or crusting.  |
| 3 - Moderate     | Clearly perceptible erythema (dull red), clearly perceptible induration/papulation, and/or clearly perceptible lichenification. Oozing and crusting may be present.                                     |
| 4 - Severe       | Marked erythema (deep or bright red), marked induration/papulation, and/or marked lichenification. Disease is widespread in extent. Oozing or crusting may be present.                                  |

IGA = Investigator's Global Assessment

The change from baseline in IGA score at each study visit is analyzed using similar MMRM model as the primary efficacy endpoint except the baseline IGA score will be included as a covariate.

The patient achieves an IGA score of 0 or 1 combined with an improvement of 2 or more points from baseline within 4 weeks of the start of treatment is analyzed as categorical variable using logistic regression.

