#### 12.4.4.4. Peak Pruritus Numerical Rating Scale (PP-NRS)

The PP-NRS ([Yosipovitch et al 2019](#)) is a single patient-reported item designed to measure peak pruritus, or ‘worst’ itch, over the previous 24 hours based on the following question: ‘On a scale of 0 to 10, with 0 being “no itch” and 10 being “worst itch imaginable,” how would you rate your itch at the worst moment during the previous 24 hours?’.

Prior to study medication application on Day 1, the study coordinator should show the PP-NRS scale to the patient, explain the scale and ask the patient to indicate which integer best describes the worst pruritus the subject experienced for their AD over the previous 24 hours.

The patient will complete this assessment and record in their diary each morning before applying study medication during the Treatment Period.

The patient will report the diary rating to site staff at each visit, who will enter it into the patient’s source documents and eCRF.

The PP-NRS score on Day 1 prior to study medication application is the baseline. The PP-NRS scores just prior to study medication application on Day 8, Day 15 and Day 28 will be flagged and used in the efficacy analysis. PP-NRS results and corresponding change from study baseline values will be summarized at each time point using descriptive statistics by treatment group. The change from baseline in PP-NRS is analyzed using similar MMRM model as the primary efficacy endpoint.

All PP-NRS score data will be presented in a data listing, the values included in the efficacy analysis will be flagged.

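### The SAP never names baseline PP-NRS as a covariate for the PP-NRS change model; on the most natural reading that model adjusts for baseline EASI instead, at some cost in precision

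*SAP*

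**What the plan says.** The primary MMRM (SAP 12.4.3.4) has treatment, visit, their interaction and AD severity as categorical terms, with baseline EASI as the continuous covariate. The SAS code in that section lists the same terms.

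The other continuous endpoints refer back to that model:

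- **IGA (SAP 12.4.4.2):** the change "is analyzed using similar MMRM model as the primary efficacy endpoint except the baseline IGA score will be included as a covariate".
- **BSA (SAP 12.4.4.3):** a model similar to the primary one, with no exception stated.
- **PP-NRS (SAP 12.4.4.4):** "The change from baseline in PP-NRS is analyzed using similar MMRM model as the primary efficacy endpoint", again with no exception. The same section defines the Day 1 pre-application score as the PP-NRS baseline.

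The predetermined covariates in SAP 9.3 are AD severity and "Continuous baseline severity EASI score/BSA score/IGA score", plus a BSA category for the PK plots. The collinearity rule in SAP 12 names the same three continuous baselines. Protocol 9.4.5 says only that IGA, BSA and PP-NRS get a model similar to the primary one.

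On testing, SAP 12 says: "Statistical hypothesis testing will be one-sided and carried out at the 5% level of significance". It covers the primary endpoint and, as appropriate, the secondary endpoints, without multiplicity adjustment.

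**The concern.** In a change-from-baseline analysis the endpoint's own baseline is usually the most useful covariate, because patients with high baseline itch tend to fall further through regression to the mean. If it is left out, whatever baseline itch difference arises by chance between two small arms (about 25 each under the current protocol, 21 each under the SAP's 42) passes partly into the estimated treatment difference. Over repeated randomisations this appears as a larger standard error. These are one cost seen from two sides.

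PP-NRS is the only patient-reported efficacy endpoint; EASI, IGA and BSA are rated by the investigator or a designee. If *similar* is read loosely instead, the covariate is simply unspecified, and the choice could be made after unblinding for an endpoint that may be tested at one-sided 5%.

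**Working it through.** **The plan's own figure.** The only power calculation is for EASI: "Data from 34 patients provides 95.6% power to detect a statistically significant difference between the treatment groups in the primary endpoint". It "assumes group means of 65% and 20% for ATI-1777 and vehicle, respectively", a difference of 45, and adds: "The variance for the percent change from baseline in EASI was assumed to be 38.3" percent. In SAP 8.4 "eligible patients will be randomly assigned in a 1:1 ratio", so 34 evaluable patients means 17 per arm. The 38.3 works only as an SD. The noncentrality is 45 / [38.3 × √(2/17)] = 45 / 13.14 = 3.43 on 32 df, and the noncentral t at one-sided 5% gives 95.61%. The stated 95.6% is reproduced (two-sided 5% would give 91.3%). It says nothing about PP-NRS, for which the documents give no SD, correlation or power.

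**Assumptions for PP-NRS (none is in the documents).**

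- ρ = correlation of baseline with Week 4 PP-NRS.
- r = correlation of baseline EASI with baseline PP-NRS.
- Baseline and Week 4 SDs are equal, and variances are in units of the PP-NRS variance.
- EASI is related to Week 4 itch only through baseline itch.
- The formulas take Week 4 alone and leave AD severity out.

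**Residual variance of the change score.**

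- Adjusted for baseline EASI: V_E = 2(1−ρ) − [r(1−ρ)]²
- Adjusted for baseline PP-NRS: V_own = 1 − ρ²
- Excess: V_E − V_own = (1−ρ)²(1−r²), which is never negative

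With unequal SDs (s_b at baseline, s_f at Week 4) the excess is (s_b − ρs_f)²(1−r²). It is zero when the slope of Week 4 on baseline itch, ρs_f/s_b, equals 1.

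**Results at r = 0.3.** The last column takes a comparison that has 80% power with own-baseline adjustment and gives Φ[(0.842 + 1.645)/SE ratio − 1.645], its approximate power under EASI adjustment at one-sided 5%.

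| ρ | V_E | V_own | V_E / V_own | SE ratio | Power |
|---|---|---|---|---|---|
| 0.3 | 1.40 − 0.0441 = 1.3559 | 0.91 | 1.490 | 1.22 | 65% |
| 0.5 | 1.00 − 0.0225 = 0.9775 | 0.75 | 1.303 | 1.14 | 70% |
| 0.7 | 0.60 − 0.0081 = 0.5919 | 0.51 | 1.161 | 1.08 | 75% |

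Over ρ from 0.2 to 0.8 and r from 0 to 0.5:

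- Worst case (ρ 0.2, r 0): 1.60/0.96 = 1.667, SE ratio 1.29.
- Mildest case (ρ 0.8, r 0.5): 0.39/0.36 = 1.083, SE ratio 1.04.

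**Chance imbalance.** With baseline EASI balanced, a 1-point baseline itch difference shifts the EASI-adjusted estimate by 1−ρ = 0.7, 0.5 or 0.3 points in the opposite direction. Allowing for the EASI difference that tends to accompany it, the shift is (1−ρ)(1−r²) = 0.64, 0.46 or 0.27. With own-baseline adjustment it is about zero.

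**Simulation check.** This used a three-visit unstructured repeated-measures fit with an AD severity term, 17 per arm and r = 0.3, for ρ = 0.3 and 0.5 only. The empirical SE ratios were 1.27 and 1.14, and the mean model-based SE ratios 1.22 and 1.14. The shift per point of itch imbalance was −0.67 and −0.45 under EASI adjustment, against about −0.02 with own-baseline adjustment.

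**The case against.** The best defence is that *similar* does not mean identical. Where the SAP means the identical model it says so, as in SAP 12.4.4.1 for EASI at the other visits. BSA has the same bare wording as PP-NRS, yet continuous baseline BSA is on the list in SAP 9.3, and its evident use is the BSA model. The logistic models also take the baseline value as a covariate. So the authors may have intended each endpoint's own baseline throughout. This stands in part: a reader might infer that the SAP states that PP-NRS is adjusted for baseline EASI, and it does not. But BSA is rescued by the list in 9.3, and PP-NRS is on neither that list nor the collinearity rule.

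A reader might also compare with an unadjusted change score. Then the variance ratio is (1+ρ)/2, and ρ of 0.3 to 0.6 gives a 12% to 24% larger SE, as if 20% to 35% of patients were discarded. That comparator is not the model the SAP points to, which carries baseline EASI and AD severity; any correlation between these and baseline itch reduces the loss.

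Finally, PP-NRS is one of several secondary endpoints in a Phase 2a trial with a preliminary efficacy objective. SAP 12.4.4.4 also has PP-NRS values and changes summarised by arm, so an imbalance could be seen. Both are true and limit the weight of the point. Seeing an imbalance does not remove it from the model estimate.

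**Conclusion.** The point holds as an omission: baseline PP-NRS is nowhere named as a covariate, and the most natural reading leaves it out of its own change model. Under the assumptions listed, the SE is about 22%, 14% or 8% larger than it need be at r = 0.3 and ρ = 0.3, 0.5 or 0.7, and 4% to 29% larger over the wider range. Every combination tried went the same way, but the size rests on correlations absent from the documents, and the loss vanishes if the slope of Week 4 on baseline itch is 1.

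Two further inferences are not supported. The estimate is not biased: randomisation balances baseline itch on average, and the shift is conditional on the observed baselines. Nor is the trial's power weakened: the primary EASI analysis uses its own baseline, and the 95.6% figure is untouched. The effect is confined to the precision and interpretation of secondary endpoints. It is worth correcting because the correction is nearly free.

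**What to change.** Before database lock and unblinding, amend the SAP as follows:

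- **9.3:** add baseline PP-NRS to the continuous baseline covariates.
- **12 (collinearity rule):** add baseline PP-NRS to the scores it covers.
- **12.4.4.4:** state that the PP-NRS MMRM has the primary model's terms, with Day 1 PP-NRS replacing baseline EASI and AD severity retained.
- **12.4.4.3:** state that baseline BSA replaces baseline EASI in the BSA MMRM, so that this section agrees with 9.3.

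The cost is a few sentences. Each change swaps one continuous covariate for another, so no model parameter is added. The Day 1 scores are already collected, and the approach follows the precedent set for IGA.

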### 12.5. PK Analyses

The PK endpoint is the concentration of ATI-1777 in plasma samples obtained using a sparse sampling approach.

Concentrations that are below the limit of quantitation (BLQ) will be treated as zero for the computation of descriptive statistics. Individual and mean plasma concentrations at each nominal sampling time point or time window for ATI-1777 will be listed and summarized in a tabular form including means, geometric means, ranges, SD, and coefficients of variation. Mean concentrations will be plotted versus nominal time on linear and semilogarithmic scales.

Plasma concentration-time profiles of ATI-1777 will be plotted on semi-log and linear scales for each individual patient as spaghetti plots using actual collection times by visit day. For ease of presentation, mean plasma concentration-time data of ATI-1777 will be plotted by nominal time on both linear and semi-logarithmic scales by visit day. Plasma PK concentrations of ATI-1777 for each patient will be reported to the precision of the raw data in listing presentations. In addition, concentration-time profiles will be plotted by patient.

If concentration data show that sufficient samples are available with quantifiable levels of ATI-1777, scatterplots of plasma concentration values versus EASI scores or baseline BMI values will be generated by visit and PK time. For Day 28, separate scatterplots will be produced by subgroup and PK time.

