1.3.2 Potential Risks

Potential risks are derived from information provided in the product labels for JAK inhibitors approved in oral dose forms for indications other than AD. Tofacitinib, upadacitinib, and baricitinib are approved for the treatment of rheumatoid arthritis; tofacitinib is also approved for the treatment of psoriatic arthritis and ulcerative colitis; and ruxolitinib is approved for the treatment of myelofibrosis and polycythemia vera. ATI-1777 is designed to be metabolically labile with limited systemic exposure to minimize these systemic toxicities. There were no ATI-1777-related dermal or systemic effects observed following repeated daily dermal applications to minipigs for up to 28 days, where little or no quantifiable systemic exposure was observed. Effects observed after repeated oral administration of ATI-1777 to rats, which achieved substantial and dose-related systemic exposure to ATI-1777, were considered to represent a spectrum of clinical effects known to be associated with oral JAK inhibitors.

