The PK of ATI-1777 will be preliminarily evaluated by measurement of ATI-1777 concentrations in plasma samples obtained using a sparse sampling schedule. A sparse sampling approach is being employed because it is not anticipated that clinically relevant plasma concentrations will be observed.

Actual time of PK sample collection, the time of last application of study medication, and the volume of study medication applied in the last study medication application must be collected in the eCRF.

A total of 8 PK samples will be collected from each patient.

One sample will be collected before study medication application and 1 sample will be collected approximately 2 hours after application on each of Days 1, 8, and 15.

Samples for Day 28 will be collected from 3 subgroups of patients within each of the specified time windows as follows:

- Subgroup 1: One sample predose and one sample at 0.5 to 2.5 hours post application

- Subgroup 2: One sample at 2.5 to 5 hours post application and one sample at least 2 hours later
- Subgroup 3: One sample at 5 to 8 hours post application and one sample at least 2 hours later (prior to the subsequent application)

The IXRS system will be used to randomly assign patients to subgroups.

The plasma samples will be analyzed for ATI-1777 using a validated assay. Samples will be used to evaluate the PK of ATI-1777. Each plasma sample will be divided into 2 aliquots (1 each for PK and a backup).

Detailed instructions for the PK blood collection, labeling, processing, storage, and shipping will be provided to the site in the Laboratory Manual.

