Treatment group comparisons for categorical efficacy endpoints (IGA Response, EASI-50, EASI-75, and EASI-90) that are conducted over time will employ a logistic regression model fit at each scheduled visit separately, where appropriate. The logistic regression model will include treatment group as a factor and the baseline value and/or baseline severity of AD as a covariate. Model-based point estimates for the treatment proportions will be provided as well as model-based differences and corresponding 90% confidence intervals and 1-sided p-values.

9.4.6 *Analysis of Safety*

The FAS will be used for the analysis of safety data (AEs, clinical laboratory, vital signs, physical examination results, and ECGs).

AEs will be coded with MedDRA. TEAEs are defined as AEs with onset dates on or after the date of first administration of study medication through the end of the study, or that exist prior to the first dose and worsen with dosing. TEAEs will be presented by system organ class and preferred term in frequency tables. Patients with multiple AEs will be counted only once within each preferred term and system organ class. Key patient information for patients with an AE with an outcome of death, patients with SAEs, and patients with an AE leading to discontinuation of study medication will be listed.

Laboratory data (hematology, serum chemistry, and urinalysis) will be converted to Système International units for reporting and processing purposes. Absolute values and changes from baseline will be presented descriptively. Laboratory data outside study-specific reference ranges will be listed.

Vital signs and ECG parameters will be presented descriptively.

9.4.7 *Demographic and Baseline Characteristics*

Demographic characteristics (including age, sex, ethnicity, and race) and baseline characteristics (including height, weight, and disease characteristics) will be presented descriptively.

9.4.8 *Pharmacokinetic Endpoints*

Individual and mean plasma concentrations at each sampling time point for ATI-1777 will be listed and summarized in a tabular form including means, geometric means, ranges, standard deviations, and coefficients of variation. Mean concentrations will be plotted versus nominal time on linear and semilogarithmic scales.

9.4.9 *Handling of Missing Values*

Patients who discontinue study medication will be asked to come to each visit for the scheduled assessments up to the end of the study.

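### Setting BLQ concentrations to zero makes the required geometric mean zero or undefined at any PK time point with even one BLQ sample

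*SAP*

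**What the plan says.** SAP 12.5 (PK Analyses) states: "Concentrations that are below the limit of quantitation (BLQ) will be treated as zero for the computation of descriptive statistics". The following sentence requires concentrations at each nominal time point or window to be "summarized in a tabular form including means, geometric means, ranges, SD, and coefficients of variation". Protocol 9.4.8 asks for the same set, "summarized in a tabular form including means, geometric means, ranges, standard deviations, and coefficients of variation", and has no BLQ rule.

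SAP 12.5 also requires log-scale graphics. For means: "Mean concentrations will be plotted versus nominal time on linear and semilogarithmic scales". For individual profiles, they "will be plotted on semi-log and linear scales for each individual patient as spaghetti plots".

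On expected levels, Protocol 6.4 justifies sparse sampling because "it is not anticipated that clinically relevant plasma concentrations will be observed". Protocol 4.3 expects minimal or no systemic exposure. Protocol 1.3.2 describes repeated dermal dosing in minipigs "where little or no quantifiable systemic exposure was observed". SAP 12.5 makes its concentration scatterplots depend on there being enough quantifiable samples, but puts no such condition on the geometric means.

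**The concern.** Two adjacent instructions in SAP 12.5 cannot both be followed to a useful result. The first puts zeros into the data used for every descriptive statistic. The second requests a statistic that is degenerate as soon as one zero is present. The sponsor's own expectation is that concentrations will be low, so zeros should not be rare.

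Pharmacokinetics is a secondary objective (Protocol 2.2) and plasma concentration is the PK endpoint (Protocol 3.3). Without a workable rule, whoever programs the table must choose to print zero, print nothing, or drop the zeros without saying so. These choices give very different summaries of typical exposure, and the choice would be made with the concentrations in hand. The primary efficacy analysis is not touched.

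**Working it through.** **The plan's own figure.** Neither document gives a figure on this point, so there is nothing to reproduce.

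**Definition.** GM = (x₁·x₂·…·xₙ)^(1/n) = exp[(1/n)·Σ ln xᵢ]. If any xᵢ = 0, the first form gives 0 and the second needs ln 0, which is undefined.

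**Illustration.** This used 25 simulated lognormal values (median 1, log-scale SD 0.6, arbitrary units).
- No BLQ: arithmetic mean 1.11, GM 1.00.
- One value set to zero: arithmetic mean 1.06, GM exactly 0.

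**Number of time-point cells.** Days 1, 8 and 15 each have a predose and a 2-hour sample, giving 6 cells. Day 28 has three subgroups with two samples each, giving 6 more, so 12 in all (Protocol 6.4; SAP Table 3).

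**Patients per cell.** The SAP's PK set contains active-treated patients only (SAP 9.2.3). With 1:1 allocation:
- Protocol 4.1.2: 50/2 = 25 active; about 25/3 ≈ 8 per Day 28 subgroup.
- SAP 8: 42/2 = 21 active; 21/3 = 7 per Day 28 subgroup.

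The equal three-way split is an assumption. The documents say only that patients are randomly assigned to subgroups.

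**Chance that a cell holds at least one BLQ value.** P = 1 − (1 − p)ⁿ, where p is an assumed BLQ rate, independent between patients. At p = 0.10 and n = 25: 1 − 0.9²⁵ = 0.928.

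| n | p = 1% | 5% | 10% | 25% | 50% |
|---|---|---|---|---|---|
| 25 | 22% | 72% | 93% | 99.9% | ~100% |
| 21 | 19% | 66% | 89% | 99.8% | ~100% |
| 8 | 8% | 34% | 57% | 90% | 99.6% |
| 7 | 7% | 30% | 52% | 87% | 99.2% |

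**Expected number of affected cells out of 12.** Count Day 1 predose as certain, then five full-arm cells and six Day 28 cells.
- 10%, Protocol numbers: 1 + 5(0.928) + 6(0.570) = 9.06, or 76%.
- 10%, SAP numbers: 1 + 5(0.891) + 6(0.522) = 8.59, or 72%.
- 1%, Protocol numbers: 1 + 5(0.222) + 6(0.077) = 2.57, or 21%.
- 25%, Protocol numbers: 1 + 5(0.999) + 6(0.900) = 11.40, or 95%.

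Using one rate for all cells is a simplification.

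**Day 1 predose.** All values should be BLQ. Under the rule the mean and SD are 0, the GM is 0 or undefined, the CV is 0/0, and the mean has no position on a log axis.

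**How much the choice of rule matters.** Same illustrative data. The limit of quantitation is not in the documents and is assumed to lie between 0.05 and 0.2.

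| BLQ of 25 | GM, BLQ = 0 | GM, BLQ omitted | GM, half the limit |
|---|---|---|---|
| 1 | 0 | 0.99 | 0.86–0.91 |
| 12 | 0 | 0.88 | 0.16–0.31 |

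The values replaced were not chosen as the smallest, so this table shows sensitivity to the rule. It does not measure how far omission overstates exposure.

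**The case against.** The best defence is that little is lost. PK is descriptive here, with no hypothesis test. Arithmetic means, SDs and ranges can still be computed, and the arithmetic CV fails only when every value in a cell is zero. Individual concentrations are listed, so any reader of the listings can recompute a geometric mean. At Day 1 predose a value of zero misleads nobody. All of this stands, and it limits the consequence. It does not reconcile the rule with the statistic it is applied to.

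Three stronger readings are tempting, and the documents do not support them.

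- *The rule ruins nearly every cell.* The documents give neither a limit of quantitation nor a BLQ rate. Protocol 6.4 speaks of clinically relevant concentrations, which is not the same as quantifiable ones, and Protocol 1.1.5 reports measured minipig mean Cmax values of 3.77 and 1.99 ng/mL. Half of the cells are small Day 28 subgroups. At 10% BLQ about three quarters of cells are affected; nearly all would need a rate of about 25% or more.
- *The semi-log plots fail in the same way.* The zero rule is worded for descriptive statistics. For individual profiles, BLQ handling is unspecified, which is a gap and not a contradiction. A plotted arithmetic mean stays positive unless the whole cell is BLQ.
- *The study cannot show that levels stay below about 45 ng/mL.* That question (Protocol 1.2) turns on the highest values. The planned ranges and listings already show them, and zeros leave the maximum unchanged whenever any sample is quantifiable. A geometric mean would not answer it under any BLQ rule.

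**Conclusion.** The point holds as a conflict between a stated rule and a required statistic in SAP 12.5, with no exception in either document. The geometric mean is zero or undefined in any cell with at least one BLQ value. That is expected at Day 1 predose. At an assumed 10% BLQ rate it has a 93% chance in a full-arm cell of 25, 89% with 21, and 52–57% in a Day 28 cell of 7–8. These figures rest on the assumed rate, independence between patients and an equal subgroup split. The degeneracy itself needs none of these assumptions.

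The effect is confined to the geometric means, to any geometric CV (the SAP does not say which CV it intends), and to the undefined treatment of BLQ values on log axes. It is worth correcting before the concentrations are unblinded, because the workable alternatives give materially different values.

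**What to change.** Amend SAP 12.5 to say:

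1. BLQ values are set to zero for arithmetic statistics only.
2. Geometric means, and a geometric CV if one is reported, use quantifiable values only. Each time point or window shows the number quantifiable and the n and % BLQ.
3. When fewer than half of the values in a cell are quantifiable, the geometric mean is reported as *not calculated*.
4. BLQ points, and means from cells that are entirely BLQ, are omitted from semi-log plots.

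In the illustration, 12 BLQ of 25 leaves 13 quantifiable (52%), so a value is shown. With 20 BLQ of 25, 5 remain (20%) and it is not.

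The drawback is that a geometric mean of quantifiable values overstates typical exposure, which is why the % BLQ must stand beside it. The cost is a few lines of SAP text and the added BLQ counts in the summary table, with no change to sampling or data collection. A count of patients at or above 45 ng/mL would be a separate analysis and is not needed for this repair.
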